4.1 Inclusion Criteria

- 4.1.1 A diagnosis of synovial sarcoma and myxoid/ round cell liposarcoma
- 4.1.2 Male or female subject, 18 or older
- **4.1.3** A superficial tumor easily and safely accessible for a research biopsy or are being considered for resection or biopsy of their tumor as part of standard of care and have recent pathology.
- **4.1.4** Zubrod performance status of '0-2' or Karnofsky score >60%. (Appendix A)
- **4.1.5** No treatment with systemic anti-cancer treatment (chemotherapy or biologics) within 2 weeks of starting interferon gamma.
- **4.1.6** Patients with a history of coronary artery disease must have had a normal stress test within 180 days of starting IFNγ.
- **4.1.7**. Must have been off metformin for at least 2 weeks prior to starting IFNγ.
- **4.1.8** No use of full dose, therapeutic anti-coagulation. However, low dose warfarin for catheter prophylaxis or acetylsalicylic acid are acceptable.
- **4.1.9** No thrombotic event within 6 months (deep vein thrombosis, pulmonary embolism) of starting IFNγ.

4.2 Exclusion Criteria

- 4.2.1 Active infection requiring oral or intravenous antibiotics
- **4.2.2** Pregnant women, nursing mothers, men or women of reproductive ability who are unwilling to use effective contraception or abstinence. Women of childbearing potential must have a negative pregnancy test within two weeks prior to entry.
- **4.2.3** Serum creatinine > 1.5 mg/dL or Glomerular Filtration Rate <50.
- **4.2.4** Significant hepatic dysfunction (SGOT > 150 IU or > 3x upper limit of normal; bilirubin > 1.6 mg/dL; prothrombin time > 1.5 x control).
- **4.2.5** Known CNS metastasis. Once CNS metastasis have been treated these patients may participate if they are otherwise good trial candidates.
- **4.2.6** Current treatment with steroids (must be discontinued 1 week before starting IFN γ).
- **4.2.7** Hemoglobin A1C >8.5%.
- **4.2.8** Uncontrolled hypertension, BP >150/100mmHg. Patients with elevated BP may enroll once BP is corrected.
- **4.2.9** NY-ESO-1 specific T cell therapy within 1 year of starting on the trial.
- **4.2.10** New (<6 months) cardiac arrhythmia (EKG should be performed within 2 weeks of starting IFN γ .
- **4.2.11** History of clinically significant congestive heart failure.

5. STUDY AGENT

Low Dose Weekly IFN_γ

Interferon gamma 1b (Actimmune) is FDA approved for the treatment of Chronic Granulomatous Disease and Osteopetrosis. Although it has been extensively studied for the treatment of cancer, it is not FDA approved for the treatment of cancer and is not considered a standard treatment for patients with sarcoma.

IFN γ will be given by sub-cutaneous administration at a dose of 0.1mg/m^2 on one of the two schedules described in the study design section prior to surgery. Patients or their caregiver will be instructed on subcutaneous self-administration.

6. INVESTIGATIONAL PLAN

All patients will have available tissue prior to study entry. The first two patients will receive low dose IFN γ (0.1mg/m²) by sub-cutaneous administration at a dose of 0.1mg/m² for four weeks prior to surgery. Injection should be given every 7 days though an allowance of 2 days before or after will be acceptable to accommodate specific circumstance. Any deviation from the recommended schedule of IFN γ dosing must be discussed with the PI. Patients or their caregiver will be instructed on subcutaneous self-administration. The last

dose of IFN γ will be given 24-48 hours prior to surgery (absolutely not more than 72 hours).

10 patients will be treated on this regimen.

Paraffin embedded tissue will be tested for class I MHC, class II MHC and NY-ESO-1. Immune infiltrates in tumors will be studied using IHC staining for CD3, CD4, CD8, CD57, CD68 and FoxP3. Antibody responses will be examined by [name] (Tisch Cancer Center). In patients with the HLA types A0201 and A2402 antigen specific T cell responses to NY-ESO-1 will be examined using MHC tetramers in the peripheral blood. In patients with the HLA type A0201, PRAME, MAGE family and CAMEL specific T cell responses will also be examined using MHC tetramers. In patients will large tumors that are resected, immune infiltrates will be examined directly by flow cytometry for markers of T cell memory (CD45RO, CD27, CD28, CCR7, CD62L, CD127) and when possible look for tumor infiltrating antigen specific T cells using MHC tetramers. When enough tumor is available RNA will also be extracted for possible future analysis.

Toxicity will be recorded and graded according to the NCI CTCAE v 4.0 at each visit.

7. MANAGEMENT OF TOXICITIES AND COMPLICATIONS

7.1 Criteria for Discontinuation of Therapy

Toxicity grading will be evaluated according to guidelines in NCI Common Toxicity Criteria version 4.0 [36]. Therapy will be discontinued in the following circumstances:

- 1. life threatening toxicity that is potentially a result of IFN γ
- 2. toxicity resulting in hospitalization
- 3. Grade 3 toxicity
- 4. Unexpected Grade 2 or greater toxicity
- 5. Expected Grade 2 toxicity lasting for over 48 hours at Grade 2 or requiring hospitalization with the exception of grade 2 cytopenias which may last >48 hours.

Expected Toxicities:

- i. Flu-like symptoms (headache, muscle ache, joint ache, chills)
- ii. Redness, pain and swelling at injection site
- iii. fatigue
- iv. rash
- v. nausea/emesis
- vi. abdominal pain
- vii. diarrhea
- viii. fever
- ix. cytopenia (anemia, lymphopenia, leukopenia may last >48 hours)

If expected toxicities progress to grade 3 (including cytopenias), the patient will be discontinued from study.

Patients discontinued from the study will not be considered in any subsequent data analysis other than toxicity data.

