The low doses of IFN γ proposed in this study (0.1mg/m² weekly) were examined in 19 patients who received up to six months of therapy. No patients on this study had grade 3 or grade 4 toxicity. The most common toxicity were flu-like symptoms (grade 1). Grade 2 toxicities included fever (2 patients) as well as chills, myalgias, flu-like symptoms and leukopenia (1 patient each). IFN γ has also been used in prior trials safely in the perioperative period both right before surgery [25] and after surgery [26].

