7.2 Concomitant Therapy

All medical problems that should occur on the trial should be treated according to the standard of care. Patients are not allowed to have anti-cancer therapy (chemotherapy, radiation, biologics) while on study. If a patient developed any medical issues that require steroids, this will be reported in all analysis of data.

7.3 **Premature Discontinuation**

Subjects who do not complete the study medication will be considered to have prematurely discontinued the study. The reasons for premature discontinuation (for example, voluntary withdrawal, toxicity, death) must be reported on the case report form. A subject may reenter the study after premature discontinuation only by approval of the Principal Investigator. If possible, final study evaluations should be completed at the time of discontinuation. Potential reasons for premature discontinuation include:

7.3.1 The development of a life-threatening infection.

7.3.2 Judgment of the principal investigator that the patient is too ill to continue.

7.3.3 Patient noncompliance with study therapy and/or clinic appointments.

7.3.4 Pregnancy.

7.3.5 Voluntary withdrawal; a patient may remove himself/herself from the study at any time without prejudice.

7.3.6 Significant and rapid progression of sarcoma requiring alternative medical or surgical intervention including, but not limited to, the development of CNS metastasis.

7.3.7 Toxicity as per section 7.1.

7.3.8 Termination of the study by the principal investigator, Institutional Review Office or the Food and Drug Administration.

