8.3 Schedule of Evaluations

History and Physical Exam: Before starting IFN γ , 24-48 hours after first IFN γ dose, every 2 weeks while on IFN γ , within 48 hours prior to surgery (if not already part of the every other weekly evaluations), 2 weeks following surgery.

CBC with differential and platelet count, CMP, Hepatic panel, and research labs – With each history and physical exam

Tumor tissue – to be obtained at time of surgery or biopsy

Research labs will typically include 40mL in green top (heparinized) tubes and 10 mL in red top (non-heparinized) tubes and will typically be drawn only at each history and physical exam. However, up to 60 mL in green top tubes and up to 20 mL in red top tubes may be drawn as often as every week if there is a scientific rationale to sample more blood for an individual patient at the discretion of the PI.

9. **REPORTING ADVERSE EVENTS**

All unexpected and serious adverse events that may be due to study treatment or intervention must be reported to the FHCRC Institutional Review Office as soon as possible but within at least 10 calendar days of the investigator learning of the event.

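### Section 7.1 drops patients discontinued from the study from every non-toxicity analysis, even when a usable in-window pre/post tumour pair exists

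*Combined protocol and SAP*

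**What the plan says.** **Exclusion.** Section 7.1 lists reasons for stopping therapy and then adds: "If expected toxicities progress to grade 3 (including cytopenias), the patient will be discontinued from study". The next sentence is the exclusion rule: "Patients discontinued from the study will not be considered in any subsequent data analysis other than toxicity data".

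**Who counts as discontinued.** Section 7.3 (Premature Discontinuation) uses a wider definition: "Subjects who do not complete the study medication will be considered to have prematurely discontinued the study". It includes toxicity under 7.1 and rapid progression among the reasons. It also asks for final evaluations at discontinuation where possible, without naming tumour tissue.

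**Timing.** Section 6 says the last dose "will be given 24-48 hours prior to surgery (absolutely not more than 72 hours"). Section 8.3 schedules a history and physical "within 48 hours prior to surgery (if not already part of the every other weekly evaluations"), and with each one "CBC with differential and platelet count, CMP, Hepatic panel, and research labs".

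**Related rules.** Section 3 sets the same 72-hour limit on the final tumour sample and lets a patient take part with only two doses when surgery is too soon for four. It also allows replacement patients, at the PI's discretion, when there are problems with a patient's data. Section 7.2 states: "Patients are not allowed to have anti-cancer therapy (chemotherapy, radiation, biologics) while on study". It handles steroid use by requiring that it be reported in all analyses.

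**Analysis set.** Section 10 defines none. It gives a power statement for the four additional patients: over 90% for an effect size above 2.5, two-tailed alpha 0.05.

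**The concern.** The primary question is whether a biological marker changes in tumour tissue after IFN γ. A patient with an evaluable sample before treatment and another inside the window after the last dose has supplied exactly that information. Section 7.1 removes the patient if an event after the start of treatment leads to discontinuation from the study, whether or not the pair exists.

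This has two consequences. Usable pairs are thrown away in a study of ten patients. The analysed set also becomes selected on toxicity, which may be related to the strength of the biological response to an immune cytokine. If the two are related, the mean change among those retained differs from the mean among those treated. The documents do not show whether such a relation exists or which way it would run.

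Patients who stop and never have a post-treatment sample are lost under any rule and are not part of this point.

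**Working it through.** **1. Can a usable pair be lost on the narrow reading?** Take only the sentence on expected toxicity reaching grade 3.
- The last dose falls 24-48 hours before surgery (Section 6).
- A blood count falls within 48 hours before surgery (Section 8.3), so it can follow the last dose.
- A grade 3 cytopenia on that count means discontinuation from study (Section 7.1).
- If surgery still goes ahead, tissue is obtained within 72 hours of the last dose.

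The patient is fully dosed, has an in-window pair and is excluded. Section 7.3 is not needed for this. If its definition also governs 7.1, which is an inference, a patient stopped after three of four doses is excluded too, while a patient planned for two doses may take part under Section 3.

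**2. The plan's power figure.** Section 10 names no test and does not define the effect size. I assume a paired t-test with d = mean change / SD of change. Power = P(|T| > t(0.975, n−1)), where T is noncentral t with n−1 degrees of freedom and noncentrality d√n.
- n = 4, d = 2.5: noncentrality 5.00, critical value 3.182, power **0.899**. An effect size of 2.507 gives 0.90, so the plan's figure is reproduced.
- n = 3: noncentrality 4.33, critical value 4.303, power **0.619**.
- n = 7, 8 or 9 (the four new pairs plus three to five earlier ones, assumed): power above **0.999**. Losing one from seven leaves n = 6 and power 0.997.

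**3. How often might it happen (narrow reading)?** On the 19 patients previously given this dose, Section 1.7 says: "No patients on this study had grade 3 or grade 4 toxicity".
- Observed rate: 0/19 = 0%.
- One-sided 95% upper limit: 1 − 0.05^(1/19) = 14.6%.
- Chance that at least one of four is excluded: 0% at the observed rate; 1 − (1 − 0.146)^4 = 47% at the limit.

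**4. Average power lost to the rule itself, without replacement.** Let p be the exclusion rate and s the share of excluded patients who have a usable pair (assumed). Average power A(p) sums power over a Binomial(4, 1−p) number of pairs, counting fewer than two as zero. The loss is A(p(1−s)) − A(p).
- p = 0: loss 0.
- p = 0.146: A = 0.532×0.899 + 0.364×0.619 + 0.093×0.219 = 0.724. With s = 0.5, A(0.073) = 0.814 and the loss is 0.090. With s from 0.25 to 1.0 the loss is 0.045 to 0.175.
- p = 0.02 or 0.05 (assumed), s = 0.5: loss about 0.01 or 0.03.

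**5. Primary MHC analysis.** With nine pairs (five adequate so far plus four, assumed), losing one moves the effect size needed for 90% power from 1.24 to 1.34.

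**6. Possible bias.** Suppose the fraction p with the greatest toxicity tendency is removed, and that tendency correlates ρ with the marker change (bivariate normal, assumed). The shift in the retained mean is ρ·φ(c)/(1−p) SD in absolute value, with c = z(1−p). At p = 0.146 this is 0.268ρ, or 0.08 to 0.19 SD for ρ between 0.3 and 0.7. It is zero if nobody is excluded. The documents give no value or sign for ρ.

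**The case against.** The strongest reply is that the practical effect may be nil. At the observed 0/19 rate nothing is lost. The 14.6% limit comes from patients treated for up to six months and probably overstates the risk over four weeks. Section 3 allows replacement, which would restore four pairs and 0.899 power. Nothing confines the macrophage analysis to the four new patients, and Section 1.10 already regards the primary endpoint as met. All of this stands, and it limits the size of the point.

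It can also be said that the cytopenia example is narrow: the 48-hour check is tied to surgery, and 7.1 is headed as a rule about stopping therapy, so the status of a fully dosed patient is arguable. That shows a need for clarification. It does not supply an exception for usable pairs.

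A completers analysis is defensible for a mechanism study: Section 1.6 reports that class I induction took three months in one of two melanoma patients. It therefore deserves a place as a sensitivity analysis.

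A reader might infer three stronger things that the documents do not support:
- **That results so far are already selected by this rule.** The one non-evaluable patient of six is described by biopsy adequacy, and no discontinuation or replacement is reported.
- **That the replacement clause inflates the type I error.** That would need replacement driven by results. The plan does not prescribe this, and its wording reads more naturally as data quality.
- **That 7.1 is the only rule on who is analysed.** The tissue window and the two-dose minimum also limit which pairs exist.

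**Conclusion.** The point holds in a limited form. Section 7.1 is an explicit rule, and following it exactly can discard an evaluable in-window pair because of a post-treatment event. That selection is unnecessary and can bias the MHC and infiltrate results.

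The likely effect is small and of unknown direction, and the primary MHC result is little affected. The drop from 0.899 to 0.619 requires that one of the four new pairs is lost, that it is not replaced, and that the four are analysed alone. It also rests on the assumed paired t-test and effect size of 2.5. The wider exclusion of everyone who does not complete medication depends on reading 7.3 into 7.1, which the text permits but does not state. The sentence should still be changed: each of four pairs is a quarter of the data behind the only power claim in Section 10, and the correction is cheap.

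**What to change.** Replace the exclusion sentence in Section 7.1 with wording such as:

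> *All treated patients with an evaluable pre-treatment sample and a post-treatment sample taken within the protocol window after the last dose received, and before any other anti-cancer therapy, are included in the MHC and infiltrate analyses regardless of discontinuation. Pairs from patients who received fewer doses than the minimum course in Section 3 are listed and reported separately. Steroid use before the post-treatment sample is flagged, as Section 7.2 requires, with a sensitivity analysis leaving those pairs out. An analysis limited to patients who completed planned dosing is a sensitivity analysis. All other treated patients are listed with reasons.*

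Reconcile Sections 3, 7.1 and 7.3 on whether a patient planned for a two-dose course counts as having completed study medication.

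As a minor clarification, state in Section 3 that replacement is for missing or inadequate samples, is decided and recorded before that patient's results are read, and does not remove evaluable data. This can apply only to patients whose results have not yet been read.

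**Cost:** protocol wording, a short definition of sample adequacy and a dated note of each replacement decision. There are no new procedures and no change to when treatment stops. The downside is that some analysed pairs will have shorter exposure, which the completers-only analysis is there to check.

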7.2 Concomitant Therapy

All medical problems that should occur on the trial should be treated according to the standard of care. Patients are not allowed to have anti-cancer therapy (chemotherapy, radiation, biologics) while on study. If a patient developed any medical issues that require steroids, this will be reported in all analysis of data.

7.3 **Premature Discontinuation**

Subjects who do not complete the study medication will be considered to have prematurely discontinued the study. The reasons for premature discontinuation (for example, voluntary withdrawal, toxicity, death) must be reported on the case report form. A subject may reenter the study after premature discontinuation only by approval of the Principal Investigator. If possible, final study evaluations should be completed at the time of discontinuation. Potential reasons for premature discontinuation include:

7.3.1 The development of a life-threatening infection.

7.3.2 Judgment of the principal investigator that the patient is too ill to continue.

7.3.3 Patient noncompliance with study therapy and/or clinic appointments.

7.3.4 Pregnancy.

7.3.5 Voluntary withdrawal; a patient may remove himself/herself from the study at any time without prejudice.

7.3.6 Significant and rapid progression of sarcoma requiring alternative medical or surgical intervention including, but not limited to, the development of CNS metastasis.

7.3.7 Toxicity as per section 7.1.

7.3.8 Termination of the study by the principal investigator, Institutional Review Office or the Food and Drug Administration.

8. SCHEDULE OF EVALUATIONS

8.1 General Toxicity Assessment

Patients will have vital signs taken, a physical exam, a comprehensive chemistry panel and a complete blood count and differential at each planned visit. Visits will occur prior to starting IFN γ , every other week while on IFN γ , and two weeks after surgery. All adverse events \geq grade 2 will be recorded and graded according to the NCI CTCAE v 4.0.

8.2 Assessment of Tumor

Paraffin embedded tumor will be tested for MHC and other studies using IHC (see Section 6 Investigational Plan). If sufficient tumor is available some will be taken for RNA and T cell infiltrates will be expanded from the tumor for analysis. If still more tumor is available tumor cell lines may be attempted to be established and infiltrates may be analyzed by flow cytometry directly at the direction of the PI.

8.3 Schedule of Evaluations

History and Physical Exam: Before starting IFN γ , 24-48 hours after first IFN γ dose, every 2 weeks while on IFN γ , within 48 hours prior to surgery (if not already part of the every other weekly evaluations), 2 weeks following surgery.

CBC with differential and platelet count, CMP, Hepatic panel, and research labs – With each history and physical exam

Tumor tissue – to be obtained at time of surgery or biopsy

Research labs will typically include 40mL in green top (heparinized) tubes and 10 mL in red top (non-heparinized) tubes and will typically be drawn only at each history and physical exam. However, up to 60 mL in green top tubes and up to 20 mL in red top tubes may be drawn as often as every week if there is a scientific rationale to sample more blood for an individual patient at the discretion of the PI.

9. **REPORTING ADVERSE EVENTS**

All unexpected and serious adverse events that may be due to study treatment or intervention must be reported to the FHCRC Institutional Review Office as soon as possible but within at least 10 calendar days of the investigator learning of the event.

9.1 Definition of an Adverse Event

Any untoward medical occurrence in a patient or clinical investigation subject administered a pharmaceutical product, medical treatment or procedure and which does not necessarily have to have a causal relationship with this treatment.

1. Life-threatening Adverse Event

Any adverse event that places the patient, in view of the investigator, at immediate risk of death from the reaction.

2. Unexpected Adverse Event

An unexpected adverse event is an adverse event that is not described in the study protocol or informed consent.

3. Serious Adverse Event (SAE)

An SAE is any adverse event occurring that results in any of the following outcomes:

- death,
- a life-threatening adverse event (real risk of dying),
- inpatient hospitalization or prolongation of existing hospitalization,
- a persistent or significant disability/incapacity,
- a congenital anomaly,
- requires intervention to prevent permanent impairment of damage.

9.2 Attribution

- Related includes adverse events that are definitely, probably, or possibly related to the medical treatment or procedure.
- Not Related includes adverse events are doubtfully related or clearly not related to the medical treatment or procedure.

9.3 **Procedure for Reporting Serious Adverse Events**

The FHCRC Serious Adverse Event (SAE) Report Form will be completed for all serious adverse events (unexpected which may be related to study treatment) that meet the expedited reporting requirements. The SAE form will be faxed to the IRO at [contact]. All available information should be submitted but it is acceptable to fax an incomplete report form at the initial report. A completed report should be faxed as soon as possible but must be received within 10 calendar days.

Unexpected serious adverse events that do not meet the requirement for expedited reporting must be reported to the IRB as part of the annual renewal of the protocol.

Scrious Adverse Events with also be reported to Horizon Pharma, who will now be supplying Interferon Gamma for the study.

9.4 Evaluation and Reporting of Adverse Events:

Patients are monitored for the development of end organ damage by assessing adverse events with serum chemistries, liver function studies, complete blood counts, and physical exams performed accordingly as explained in **Section 8.3**.

We will report any adverse events related to IFN γ that are unexpected (see expected toxicities in 7.1), serious (grade 2 or higher) or result in the discontinuation of therapy. See **Section 7.1** regarding criterion for discontinuation of therapy. IFN γ is an approved drug that has been used in hundreds of cancer patients and has an established record of expected toxicities. All adverse events for all systems are graded on a scale of 1-5 and attribution is assigned, using the NCI Common Terminology Criteria for Adverse Events (version 4).

